#### **Surgeries – Imputation Rules.**

If reported surgery date is a full valid date then set start date equal to the date part of surgery date.

In case of partial date, use one of the two imputation rules described below:

A. For data collected on "PRIOR SURGERY RELATED TO CANCER" CRF page:

• If only day is missing then impute as the first day of the month;

- If both day and month are missing then then impute as 01JAN of the year;
- If date is completely missing or invalid then leave missing.
- B. For data collected on other CRF pages (deemed to be on-treatment/subsequent surgeries):
- If only day is missing then
  - If month and year of surgery match month and year of first dose date then impute the missing date as the date of first dose;
  - If month and year of surgery don't match month and year of first dose date then impute as first day of that month and year;
- If both day and month are missing then impute as maximum between 01JAN of the year and date of the first dose;
- If date is completely missing or invalid then leave missing.

#### **APPENDIX 3**

TIME-TO ONSET AND TIME-TO RESOLUTION DEFINITION AND CONVENTIONS FOR SELECT ADVERSE EVENTS, IMMUNE-MEDIATED ADVERSE EVENTS AND EVENTS OF SPECIAL INTEREST

#### **Time-to onset definition**

Time-to onset of AE (any grade) for a specific category is defined as the time between the day of the first dose of study treatment and the onset date of the earliest AE (of any grade) in this category.

The time-to onset of AE (grade 3-5) for a specific category is defined similarly with an onset date corresponding to a grade 3-5 AE.

Time-to onset of drug-related AE (any grade or grade 3-5) for a specific category is defined similarly but restricted to drug-related AE.

Time-to onset for a specific subcategory is defined similarly but restricted to event of this subcategory.

#### **Time-to resolution definition**

In order to derive the time-to resolution, overlapping or contiguous AEs within a specific category or subcategory will be collapsed into what will be termed "clustered" AEs. For example, if a subject (without pre-treatment AE) experienced an AE from 1st to 5th January, another AE (with different PT but within same category) from 6th to 11th January and same AE from 10th to 12th January, these will be collapsed into one clustered AE from 1st to 12th January. Table 10-5 is summarizing key derivation steps for each type of clustered AEs.

Time-to resolution of AE (any grade) for a specific category is defined as the longest time from onset to complete resolution or improvement to the grade at baseline among all clustered AEs experienced by the subject in this category per adverse event criteria category. Events which worsened into grade 5 events (death) or have a resolution date equal to the date of death are considered unresolved. If a clustered AE is considered as unresolved, the resolution date will be censored to the last known alive date. Improvement to the grade at baseline implies that all different events in the clustered adverse event should at least have improved to the corresponding (i.e. with same preferred term) baseline grade. This measure is defined only for subjects who experienced at least one AE in the specific category.

The time-to resolution of AE (grade 3-5) for a specific category is defined similarly with an onset date corresponding to a grade 3-5 AE.

Time-to resolution of drug-related AE (any grade or grade 3-5) for a specific category is defined similarly but restricted to drug-related AE.

The time-to resolution of AE (any grade or grade 3-5, drug-related or all) where immune modulating medication was initiated is defined similarly. For data presentation not restricted to IMAE, the additional condition that the subject started an immune modulating medication during the longest AE resolution period will be applied.

Time-to resolution for a specific subcategory is defined similarly but restricted to event of this subcategory.

Table 10-5: Derivation of clustered AE

Type of clustered AE	Derivation
Any grade	Collapse any on-treatment AE from the same category
Drug-related of any grade	Collapse any on-treatment drug-related AE from the same category
Grade 3-5	Collapse any on-treatment AE from the same category.  Resolution will be based on the onset date of the earliest grade 3-5 records (if no grade 3-5 record, clustered AE is excluded)
Drug-related of Grade 3-5	Collapse any on-treatment drug-related AE from the same category  Resolution will be based on the onset date of the earliest grade 3-5 record (if no Grade 3-5 record, clustered AE is excluded)

The algorithm for collapsing adverse event records is using the following conventions:

For each subject and specified category, the corresponding adverse event records will be collapsed when:

- 1) Multiple adverse event records have the same onset date.
- 2) The onset date of an event record is either the same day or 1 day later than the resolution date of a preceding event record (contiguous events).
- 3) The onset date of an event record is after the onset date and prior to or on the resolution date of a preceding event record (overlapping events).

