#### 7.6.6.3 Time-to Resolution of Select AE

Time-to resolution of the following specific events will be summarized separately for each category/subcategory.

- Time-to resolution of drug-related select AE (any grade, grade 3-5) by treatment group
- Time-to resolution of drug-related select AE (any grade, grade 3-5) where immune modulating medication was initiated, by treatment group

Time-to resolution analyses are restricted to treated subjects who experienced the specific events. Time-to resolution where immune modulating medication was initiated analyses are restricted to treated subjects who experienced the specific events and who received immune modulating medication during the longest select AE.

The analyses will be conducted using the 30-day safety window.

The following summary statistics will be reported: percentage of subjects with resolution of the longest select AE, median time-to resolution along with 95% CI (derived from Kaplan-Meier estimation) and ranges.

See time-to resolution definition subsection of APPENDIX 3 for additional details.

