#### 7.6.10 Immune Mediated Adverse Events

IMAEs will be summarized by treatment group for each immune-mediated category / PT using the 100-day safety window:

- Overall summary of non-endocrine IMAEs by worst CTC grade (any grade, grade 3-4, grade 5) where immune modulating medication was initiated presented by Category / PT.
- Overall summary of endocrine IMAEs by worst CTC grade (any grade, grade 3-4, grade 5) presented by Category / PT.
- Overall summary of non-endocrine IMAEs leading to discontinuation by worst CTC grade (any grade, grade 3-4, grade 5) where immune modulating medication was initiated presented by Category / PT.
- Overall summary of endocrine IMAEs leading to discontinuation by worst CTC grade (any grade, grade 3-4, grade 5) presented by Category / PT.

- Overall summary of non-endocrine IMAEs leading to dose delay or reduction by worst CTC grade (any grade, grade 3-4, grade 5) where immune modulating medication was initiated presented by Category / PT
- Overall summary of endocrine IMAEs leading to dose delay or reduction by worst CTC grade (any grade, grade 3-4, grade 5) presented by Category / PT.
- Summaries of time-to onset and time-to resolution of non-endocrine IMAEs where immune modulating medication was initiated presented by Category.
- Summaries of time-to onset and time-to resolution of endocrine IMAEs presented by Category.

A by-subject listing of IMAEs will be provided. By-subject listings of time-to resolution for longest IMAEs cluster (any grade and grade 3-5 in separate summaries) will also be provided. For new studies which collect investigator assessment of potential IMAE data, a by-subject listing of AEs considered as immune-mediated events per investigator but not qualified for IMAEs definition will also be provided.

In addition, for all Nivolumab and/or Ipilimumab treated subjects who experienced at least one IMAE, the following data presentation will be provided:

• Summary of subjects who were re-challenged with Nivolumab and/or Ipilimumab by IMAE category, with extended follow-up

For these, re-challenge is considered to have occurred when last Nivolumab and/or Ipilimumab infusion was administered after the onset of an IMAE.

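### Time to resolution takes a subject's longest clustered AE by length alone, so a subject with a shorter unresolved or fatal cluster can be counted as resolved

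*SAP*

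**What the plan says.** SAP Appendix 3 (time-to resolution definition) first collapses AE records of one category into clusters. Records merge when they share an onset date, when one starts on the day another ends or on the next day, or when they overlap: "The onset date of an event record is after the onset date and prior to or on the resolution date of a preceding event record". Events separated by a longer gap stay in separate clusters.

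Each subject then contributes one value per category, "the longest time from onset to complete resolution or improvement to the grade at baseline among all clustered AEs experienced by the subject".

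Two further rules settle the status of a cluster. On deaths: "Events which worsened into grade 5 events (death) or have a resolution date equal to the date of death are considered unresolved". On length: "If a clustered AE is considered as unresolved, the resolution date will be censored to the last known alive date". Nothing in Appendix 3 says how a censored cluster ranks against a resolved one, or that an unresolved cluster takes precedence.

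For select AEs, SAP 7.6.6.3 reports "percentage of subjects with resolution of the longest select AE, median time-to resolution along with 95% CI (derived from Kaplan-Meier estimation) and ranges". For IMAEs, SAP 7.6.10 plans summaries of time to resolution by category and adds: "By-subject listings of time-to resolution for longest IMAEs cluster (any grade and grade 3-5 in separate summaries) will also be provided".

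**The concern.** The length of a cluster decides which one represents the subject, and only then does that cluster's status decide whether the subject counts as resolved. The rule that a death is unresolved therefore takes effect only if the fatal cluster happens to be the longest.

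The quantity being estimated is the maximum duration over a subject's clusters. If one cluster resolved after 60 days and another was still open when observation stopped at day 10, that maximum is at least 60 days and otherwise unknown. It should be censored at 60 days. The rule as written records an event at 60 days instead. The error runs one way only: it turns censored subjects into resolved ones and never the reverse.

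At stake are the percentage of subjects resolved and the median time to resolution, in subjects with more than one separate cluster in a category. Such subjects are to be expected. Protocol 4.5.4.1 allows treatment to resume after an AE resolves, and SAP 7.6.10 plans a summary of subjects re-challenged after an IMAE.

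**Working it through.** **1. The SAP's own example.** Records of 1-5, 6-11 and 10-12 January: the second starts the day after the first ends, and the third overlaps the second. Applying the rules gives one cluster, 1-12 January, as the SAP states.

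**2. The rule on constructed records** (dates assumed; duration = last date - first date + 1, SAP section 10). In cases A to C the first cluster runs from 1 January to 29 February 2020, 60 days, resolved.

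| Case | Later record, same category | Length | Cluster selected | Subject counted as |
|---|---|---|---|---|
| A | 1-10 April, fatal | 10 days, censored | 60 days | resolved |
| B | from 1 April, ongoing, last contact 20 April | 20 days, censored | 60 days | resolved |
| C | from 1 April, ongoing, last contact 31 December | 275 days, censored | 275 days | censored |
| D | first event never resolves, so later records merge into it | 366 days to 31 December | 366 days | censored |

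Cases A and B show the fault. Cases C and D show its limit: an open cluster with long follow-up is usually the longest and is kept as censored.

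**3. Effect on the percentage.** Take 20 subjects, each with a 60-day resolved cluster, of whom k later have a separate 10-day fatal cluster. The rule reports 20/20 = 100% whatever k is. Counting a subject as unresolved when any cluster is unresolved gives (20 - k)/20: 95% for k = 1, 90% for k = 2, 75% for k = 5.

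**4. Size under assumed inputs.** The documents give none of these, so all are assumptions: exponential time to resolution with mean 6 weeks; exponential censoring with mean 40 weeks for a first cluster and m weeks for a second; a second cluster in a fraction q of the subjects whose first cluster resolved.

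- First cluster: total rate r1 = 1/6 + 1/40 = 0.1917; probability resolved p1 = (1/6)/r1 = 0.8696.
- Second cluster: r2 = 1/6 + 1/m; p2 = (1/6)/r2.
- Under exponential times, length and status are independent, and the first cluster is the longer with probability r2/(r1 + r2).
- Overstatement of percent resolved = q × p1 × (1 - p2) × r2/(r1 + r2).
- Correct percentage = p1 × [1 - q(1 - p2)].

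| m (weeks) | q | p2 | r2/(r1+r2) | Rule as written | Correct | Overstatement (points) |
|---|---|---|---|---|---|---|
| 40 | 0.05 | 0.8696 | 0.500 | 86.7% | 86.4% | 0.28 |
| 40 | 0.20 | 0.8696 | 0.500 | 85.8% | 84.7% | 1.13 |
| 40 | 0.40 | 0.8696 | 0.500 | 84.7% | 82.4% | 2.27 |
| 20 | 0.20 | 0.7692 | 0.531 | 85.1% | 82.9% | 2.13 |
| 12 | 0.20 | 0.6667 | 0.566 | 84.4% | 81.2% | 3.28 |
| 20 | 0.40 | 0.7692 | 0.531 | 83.2% | 78.9% | 4.26 |
| 12 | 0.40 | 0.6667 | 0.566 | 81.9% | 75.4% | 6.56 |

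The last row in full: 0.40 × 0.8696 × 0.3333 × 0.566 = 0.0656. Simulation of the same inputs (400,000 subjects per row) agrees with both percentage columns to within 0.1 point. In those simulations the Kaplan-Meier median is shortened by 1% or less in the first two rows, by 2% in the third, and by about 2% to 6% in the last four.

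The fourth column is also the share of subjects with a resolved first and an unresolved second cluster whom the rule reports as resolved: 50% to 57%.

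**The case against.** The strongest reply is that the statistic is labelled for what it is. SAP 7.6.6.3 announces the "percentage of subjects with resolution of the longest select AE", so the reader is told that one cluster per subject is used, and the percentage with all clusters resolved is a different summary. That stands as a reason to keep the existing row. It does not rescue the derivation: while any cluster is open, the longest one is not known, and the label cannot make a censored maximum an observed one.

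A reader might infer that the fatal event disappears from the report. The documents do not support that. Grade 5 select AEs are tabulated and listed (SAP 7.6.6.1), as are grade 5 IMAEs (7.6.10), and deaths are summarised with reasons (7.6.1). The event is missing only from the time-to-resolution summaries.

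A reader might also infer that every subject with an open event is miscounted. Case C shows otherwise. The fault needs two separate clusters in one category, one of them unresolved and shorter than a resolved one. The grade 3-5 summaries also exclude clusters without a grade 3-5 record, so a Grade 2 event followed by a fatal one distorts the any-grade summary only. The 30-day window for select AEs limits late recurrences further. For IMAEs the window is 100 days, and no percentage resolved is specified.

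Taking the longest cluster also discards short resolved events, which lengthens the reported time compared with a per-event summary. That is true, but it belongs to the chosen estimand. Within that estimand the censoring error still runs in the favourable direction.

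Finally, the size depends on the inputs. Overstatements above 2.3 points need second events to be censored much sooner than first ones. It is tempting to justify this by saying that fatal events are short, but the documents give no durations.

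**Conclusion.** The rule is wrong as written, not merely under-specified: with a longer resolved cluster and a shorter, separate unresolved one, it counts a right-censored value as a resolution. The percentage resolved for select AEs is biased upward, and the Kaplan-Meier median for select AEs and IMAEs is biased downward.

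The size cannot be computed from the documents. Under the assumptions above, the overstatement is about 0.3 to 2.3 points when second clusters are followed as long as first ones and recur in 5% to 40%. It is about 2 to 6.5 points when their mean censoring time is 12 to 20 weeks and 20% to 40% recur.

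The documents do not support reading this as a threat to the trial's conclusions. Safety is exploratory (SAP 4.3.2), these summaries are descriptive, and no test or significance level uses them. The change is still worth making, because the bias has a known direction and is cheap to remove.

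**What to change.** Add to the time-to resolution definition in SAP Appendix 3: *If any clustered AE in the category is unresolved, the subject is censored at the longest observed duration among the clusters; otherwise the longest resolved duration is the event time.* The same sentence then governs the IMAE summaries and listings of 7.6.10.

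In 7.6.6.3, report the percentage of subjects in whom all clustered AEs of the category resolved, beside the existing longest-AE percentage and not in its place.

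The cost is SAP wording, a small derivation change and one extra row; no new data are needed. Resolution figures become slightly less favourable. The all-resolved percentage is more sensitive to events that open shortly before data cut-off, which is why both rows should be shown.

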# APPENDIX 4 IMMUNOGENICITY ANALYSIS: BACKGROUND AND RATIONALE

The following summary is from the FDA Guidance for Industry Immunogenicity Assessment for Therapeutic Protein Products and White Paper on Assessment and Reporting of the Clinical Immunogenicity of Therapeutic Proteins and Peptides – Harmonized Terminology and Tactical Recommendations by Shankar et al. The program-level definitions of sample- and subject-level ADA status are based on recommendation from the BMS Immunogenicity Council.

Immune responses to therapeutic protein products may pose problems for both patient safety and product efficacy. Immunologically based adverse events, such as anaphylaxis and infusion reactions, have caused termination of the development of therapeutic protein products or limited the use of otherwise effective therapies. Unwanted immune responses to therapeutic proteins may also neutralize the biological activity of therapeutic proteins and may result in adverse events not only by inhibiting the efficacy of the therapeutic protein product, but by cross-reacting to an endogenous protein counterpart, if present. Because most of the adverse effects resulting from elicitation of an immune response to a therapeutic protein product appear to be mediated by humoral mechanisms, circulating antibody has been the chief criterion for defining an immune response to this class of products.

ADA is defined as biologic drug-reactive antibody, including pre-existing host antibodies that are cross-reactive with the administered biologic drug (baseline ADA). Titer is a quasiquantitative expression of the level of ADA in a sample. By employing a serial dilution-based test method, titer is defined as the reciprocal of the highest dilution of the sample (e.g., dilution of 1/100 = 1/100 = 1/100). The ADA is also tested, via a cell-based biologic assay or a non cell-based competitive ligand-binding assay for a subpopulation of ADA known as neutralizing antibodies (NAb), which inhibits or reduces the pharmacological activity of the biologic drug molecule regardless of its in vivo clinical relevance. Non-neutralizing ADA (non-NAb) is ADA that binds to the biologic drug molecule but does not inhibits its pharmacological activity.

ADA should be tested using sensitive and valid methods and employing an appropriate strategy for elucidating immunogenicity. Detection of ADA is typically performed in three tiers (screening, confirmatory, and titer) using statistically determined cutpoints and samples testing positive in the ADA assay are analyzed for neutralizing activity, especially in late-stage clinical studies. "Detection" of ADA implies that drug-specific ADA was confirmed. The 'drug tolerance" of an assay (highest drug concentration that does not interfere in the ADA detection method) is not an absolute value and differs between individuals due to the varying avidities of ADA immune responses. An ADA sampling strategy of collecting samples at times when the least drug concentration is anticipated (trough concentrations) can increase the likelihood of accurate ADA detection.

It is useful to present ADA results from clinical studies as (a) characteristics of the ADA immune response, (b) relationship of ADA with pharmacokinetics (PK) and, when relevant, pharmacodynamics (PD) biomarkers, and (c) relationship of ADA with clinical safety and efficacy.

Clinical consequences of ADA can range from no apparent clinical effect to lack of efficacy (primary treatment failure), loss of efficacy (secondary treatment failure) or heightened effect due to altered exposure to the biologic drug, adverse drug reactions (administration-related systemic or site reactions), and severe adverse drug reactions (anaphylaxis and unique clinical problems associated with cross-reactivity and neutralization of endogenous molecules). Thus it becomes important to examine any associations between ADA or any of its attributes with the various clinical sequelae. The presence of ADA may or may not preclude the administration of drug to ADA-positive subjects because the outcome is dependent upon the magnitude of the impact of ADA on PK and PD. Hence, the relationship of ADA with PK/PD is an important additional consideration, but does not necessarily result in a clinically impactful consequence per se.

# **Immunogenicity Endpoints**

A fundamental metric that informs clinical immunogenicity interpretation is the incidence of ADA in a study or across comparable studies. ADA incidence is defined as the proportion of the study population found to have seroconverted or boosted their pre-existing ADA during the study period.

#### **Terms and Definitions**

Validated ADA test methods enable characterization of samples into ADA-positive vs. ADA-negative. To classify the ADA status of a subject using data from an in vitro test method, each sample from the subject is categorized based on the following definitions:

### Sample ADA Status:

- Baseline ADA-positive sample: ADA is detected in the last sample before initiation of treatment
- Baseline ADA-negative sample: ADA is not detected in the last sample before initiation of treatment
- ADA-positive sample: After initiation of treatment, (1) an ADA detected (positive seroconversion) sample in a subject for whom ADA is not detected at baseline, or (2) an ADA detected sample with ADA titer to be at least 4-fold or greater (≥) than baseline positive titer
- ADA-negative sample: After initiation of treatment, ADA not positive sample relative to baseline

Next, using the sample ADA status, subject ADA status is defined as follows:

#### **Subject ADA Status:**

- Baseline ADA-positive subject: A subject with baseline ADA-positive sample
- **ADA-positive subject**: A subject with at least one ADA positive-sample relative to baseline at any time after initiation of treatment
- 1) Persistent Positive (PP): ADA-positive sample at 2 or more consecutive time points, where the first and last ADA-positive samples are at least 16 weeks apart
- 2) Not PP-Last Sample Positive: Not persistent positive with ADA-positive sample at the last sampling time point

- 3) Other Positive: Not persistent positive but some ADA-positive samples with the last sample being negative
- 4) Neutralizing Positive: At least one ADA-positive sample with neutralizing antibodies detected
- ADA-negative subject: A subject with no ADA-positive sample after the initiation of treatment.

(Note: 16 weeks was chosen based on a long half-life of IgG4.)

